### **3. STUDY DESIGN**

We will perform a single center diagnostic accuracy study, in which patient-scans obtained using two types of PET/CT scanners (1 clinical study on the conventional system and 1 clinical study on the digital system) will be intra-individually compared.

Patient selection will be performed at the NM department in Isala. Patient eligibility will be based on the information provided by the referring specialist on the requisition for the clinical FDG-PET/CT study.

Patients will be included during the inclusion period of 6-12 months. Patients that meet the inclusion criteria and have signed informed consent will undergo two PET/CT scans on both the conventional and the digital PET system, immediately after each other. The scan order will be randomized per week:

- Week 1: first scan on conventional PET/CT, second scan on digital PET/CT.
- Week 2: first scan on digital PET/CT, second scan on conventional PET/CT. Etc.

For each patient, we start with a separate analysis of conventional and digital PET/CT images. One investigator will evaluate the PET/CT images quantitatively while two NM physicians will give qualitative (visual) judgments. Afterwards, we compare conventional and digital findings for all patients.

PET/CT data will be analyzed based on three subgroups of patients with lung cancer, breast cancer and esophageal cancer respectively. Pathology results and follow-up imaging by PET, CT, echography and MRI will be used as gold standard. When validation results are not available, conventional and digital PET/CT results are just compared with each other. More information on data analysis is described in section 5.2.

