#### **4. STUDY POPULATION**

##### **4.1 Population (base)**

During the time that the study is open, we will select consecutive patients based on the information provided by the referring physician on the requisition for the study.

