### 5.1 Study procedures

#### 5.1.1 Patient selection

During the study period, all referrals for FDG-PET/CT scans in the NM department in Isala will be evaluated by one of the investigators. Based on inclusion and exclusion criteria, the investigator makes an initial selection of patients suitable for this study. Each referral that meets the inclusion criteria will be listed. For these selected patients, we plan a informed consent talk of around 15 minutes with a NM physician, physician assistant or one of the investigators. This talk takes place prior to the first clinical FDG-PET/CT scan. More details on the informed-consent procedure are described in section 8.2 Recruitment and consent.

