#### 5.1.3 First PET/CT acquisition

Sixty minutes after FDG tracer injection, a standard clinical whole-body PET/CT scan is performed on the conventional or digital PET/CT scanner. (As mentioned in the study design, the PET scan order is randomized per week). For the first scan, the acquisition times are 1 and 2 minutes per bed position for patients with body weight up to 80 kilogram and from 81 kilogram respectively. To cover the whole-body region, on average 11 bed positions are required. This results in total PET

acquisition times of approximately 11 and 22 minutes for patients with body weight  $\leq 80$  kg and  $> 80$  kg respectively. Furthermore, attenuation CT acquisition takes around 5 minutes in all patients. Moreover, for many patients an additional diagnostic contrast-enhanced CT scan is acquired on the clinical PET/CT system with a total procedure time of approximately 15 minutes.

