### **8.2 Recruitment and consent**

During the study period, all referrals for FDG-PET/CT scans in the NM department in Isala will be evaluated by one of the investigators. Based on inclusion and exclusion criteria, the investigator makes an initial selection of patients suitable for this study. Because the time period between PET/CT referral and PET/CT acquisition is very short (only a few days), we will approach the patients when they arrive at the NM department for their clinical PET/CT scan.

During a personal talk with a NM physician, physician assistant or one of the investigators, an adequate explanation of the aims, methods, anticipated benefits, and potential hazards of the study will be provided. Furthermore, the patient receives the study information letter. The patient will be given the opportunity to discuss the participation with family and friends (if they desire) or to further review on their own prior to signing the informed-consent form. After the personal talk, the radioactive tracer FDG is injected and the patient has to wait for 60 minutes (exposure time). After this waiting period, we ask the patient to sign the informed-consent form. Subsequently the first and eventually second PET/CT scan are acquired. The patient will have at least one hour to consider his decision.

The written consent form will be revised if new information becomes available during the study that may be relevant to the subject. Any revision(s) will be submitted to the METC for review and approval in advance of use.

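### The scan order is described as randomised by week, but the written sequence is fixed weekly alternation, and the primary tests take no account of order

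*Combined protocol and SAP*

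**What the plan says.** Section 3 (Study design) gives the allocation of scan order in one sentence and two bullets. The sentence is "The scan order will be randomized per week". The bullets are "Week 1: first scan on conventional PET/CT, second scan on digital PET/CT" and "Week 2: first scan on digital PET/CT, second scan on conventional PET/CT. Etc". Section 5.1.3 refers back to the study design and repeats that "the PET scan order is randomized per week".

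On who enters the study and when:

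- Section 4.1: "we will select consecutive patients based on the information provided by the referring physician".
- Section 5.1.1: all referrals are evaluated and "the investigator makes an initial selection of patients suitable for this study"; every referral that meets the inclusion criteria is listed.
- Section 8.2: "we will approach the patients when they arrive at the NM department for their clinical PET/CT scan". FDG is then injected and the patient waits 60 minutes. "After this waiting period, we ask the patient to sign the informed-consent form".

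On the delay, section 5.1.4 expects the second scan about 21 to 47 minutes after the first and lengthens its acquisition time, patient by patient, to compensate for radioactive decay. Section 7.1.1 plans the sign test, the Wilcoxon signed-rank test and McNemar's test for the primary objective. None of them includes scan order.

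**The concern.** The label and the sequence do not agree. A sequence that switches every week contains no random element. It can be foreseen at referral, at approach and at consent, and a report that repeats the word randomised would misdescribe the design. Section 9.6 allows the results to support marketing and regulatory claims, so the description should be exact.

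The statistical issue is narrower. Being scanned second may change what is seen. If the two orders are equally represented, such an effect cancels from the comparison of scanners. If they are not, part of it is counted as a scanner difference. The planned primary tests rely entirely on balance of order, and the plan neither checks that balance nor adjusts for it. The three tumour groups are analysed separately, so balance is needed within each group, and the esophageal group has only 45 patients.

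**Working it through.** **1. Is there a random element?** Section 3 fixes weeks 1 and 2 and continues the pattern; section 5.1.3 adds no mechanism. The only other randomisation in the protocol is of the reading order for the two nuclear medicine physicians (section 5.2.2), which is a separate matter. Under the written sequence, the order in any later week follows from week 1 with probability 1. With independent weekly draws, a future week could be guessed with probability 0.5.

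**2. When is the order knowable?** The calendar week fixes it. Selection, approach and signature of consent all come before the first scan, and nothing conceals the order. That staff know the order is an inference, but a safe one.

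**3. Can order matter, on the protocol's own account?** Using the half-life of 110 minutes in section 5.1.4, the fraction of FDG remaining is 0.5^(t/110):

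| Delay (min) | Remaining, recomputed | Table 2 |
|---|---|---|
| 21 | 87.6% | 88% |
| 32 | 81.7% | 82% |
| 36 | 79.7% | 80% |
| 47 | 74.4% | 74% |

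Table 2 reproduces, and the longer acquisition addresses this decay. Even so, section 7.1.2 expects delay to influence normal-tissue uptake, and section 5.2.4 is cautious about quantitative EANM conclusions because of the delay. The only planned analysis of delay is the normal-tissue correlation, which belongs to the secondary objective.

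**4. How an imbalance would act.** Let δ be the true net scanner difference, e the net effect of being scanned second, and s the share of patients with digital second.

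- Digital second: expected difference (digital minus conventional) = δ + e
- Digital first: expected difference = δ − e
- Pooled: s(δ + e) + (1 − s)(δ − e) = δ + e(2s − 1)

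The spurious part is e(2s − 1), which is zero at s = 0.5. The documents give neither e nor s, so the values below are assumptions, and e could have either sign.

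| Assumed e | s = 0.55 | s = 0.60 | s = 0.65 |
|---|---|---|---|
| 0.05 | 0.5 points | 1 point | 1.5 points |
| 0.10 | 1 point | 2 points | 3 points |
| 0.20 | 2 points | 4 points | 6 points |

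At e = 0.10 and s = 0.60, this is 0.10 × 0.20 = 0.02, or a net 0.02 × 45 = 0.9 of an esophageal patient and 0.02 × 90 = 1.8 lung or breast patients.

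**5. Scale against the plan's target.** The stated sizes for N status, 79 and 42, are the smallest at which an exact two-sided sign test reaches the stated power when an untied patient favours one scanner with probability 0.5 + 0.16 = 0.66. That is a net 0.66 − 0.34 = 32 points among untied patients. The illustrated 2 points, counted over all patients, are small beside it. None of the sample sizes depends on how order is assigned.

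**6. Can imbalance arise without any selection?** Six to 12 months is about 26 to 52 weeks. The esophageal group then averages 45/26 = 1.7 to 45/52 = 0.9 patients per week, so alternating weeks need not give equal numbers of patients. For scale, even with a fair coin for each patient, a split at least as uneven as 27:18 (60:40) among 45 has exact two-sided probability 0.23, and at least as uneven as 54:36 among 90 has 0.07. Random allocation alone therefore does not remove the need to look at order in the analysis.

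**The case against.** The case for leaving the design alone is substantial. Every patient has both scans and both are used for diagnosis (section 5.1.6), so knowing the order cannot steer a patient to one scanner only. Selection is meant to be consecutive and eligible referrals are listed, so selective approach would depart from the protocol and could be checked against that list. Acquisition time is corrected for decay. Alternation also balances weeks well: with independent random draws, the share of conventional-first weeks would have a standard deviation of 9.8 percentage points over 26 weeks and 6.9 over 52. The bullets might also be read as an example of weekly randomisation.

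Most of this stands, and it is why the point is minor. It does not rescue the label: if the bullets are only an example, the random mechanism is still missing. Nor does it supply an order term. The decay correction is already in the plan, yet section 7.1.2 still expects an effect of delay.

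A reader might infer more: that staff will choose patients according to order, that the sequence will coincide with a two-week clinic cycle, or that the scanner comparison is invalid. The documents do not support these readings. They give no motive for selection and describe no two-week cycle, and the within-patient comparison remains intact. Nor do they show that delay changes N status; the expectation in section 7.1.2 concerns normal-tissue uptake.

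**Conclusion.** The point holds as a misdescribed allocation method together with a small gap in the analysis. Sections 3 and 5.1.3 claim randomisation, whereas the written sequence is weekly alternation, predictable throughout. This rests on the text alone.

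The bias is probably small. The range of 0.5 to 6 percentage points rests on assumed order effects and assumed splits, and should be read as an illustration rather than an estimate. Neither the sample sizes nor the power are affected. What remains is that the primary analysis has no protection if order is unbalanced within a tumour group, most plausibly the esophageal group. The point is worth correcting because correction is nearly free, not because the study is at risk.

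**What to change.** Choose one of two descriptions, and make the analysis change with either.

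1. **Randomise.** Draw each week's order from a computer-generated list held by someone who does not approach patients. This breaks any link between order and calendar weeks, but does not hide the order within a running week, because patients are approached on arrival. Balancing the list in blocks of weeks limits the chance imbalance noted above, but makes the last week of a block predictable.
2. **Or keep alternation.** Call it weekly alternation in sections 3 and 5.1.3, and do not claim randomisation of scan order in reports.

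In either case:

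- Report the numbers scanned in each order, overall and by tumour group.
- Add to section 7.1.1 an order-stratified version of the primary paired comparison. Estimate the net difference separately in digital-first and digital-second patients and average the two with equal weight: [(δ + e) + (δ − e)]/2 = δ, whatever the split.

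The cost is a short list or two wording changes, plus one added analysis. Scheduling can stay at one order per week. No new data are needed, since section 5.2.1 already records the scanner and the start time of each scan.

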## SUMMARY

**Rationale:** FDG-PET/CT imaging is important for staging, response monitoring and prognosis prediction in patients with cancer. However, the spatial resolution of current PET/CT systems is relatively low, limiting the detection of small lesions and accurate staging. In 2017, a new state-of-the-art digital PET/CT system will be installed at the NM department in Isala. It is expected that this new type of scanner contributes to more accurate staging and possibly more effective patient management. For a period of 6-12 months, both a conventional and a digital PET/CT system will be available in the NM department in Isala. This provides the unique possibility to evaluate the performance of the digital PET/CT system compared with conventional PET/CT. In this study, we will analyze the impact of digital PET/CT on the final diagnostic conclusion of the scan in patients with lung cancer, breast cancer and esophageal cancer.

**Objectives:** Primary objective: How does the diagnostic outcome of the digital PET/CT study compare to the outcome of conventional PET/CT in patients referred for (re)staging of lung cancer, breast cancer and esophageal cancer?

Secondary objective: What is the image quality (in both quantitative and qualitative terms) of digital PET as compared to conventional PET?

Both the primary and secondary objective are further specified in multiple detailed objectives.

**Study design:** Single center diagnostic accuracy study using intra-individual comparisons of PET/CT scans

**Study population:** 225 adults referred for a FDG-PET/CT scan in Isala to evaluate (suspected) lung cancer, breast cancer and esophageal cancer

**Main study parameters:** Primary: diagnostic outcome of the PET/CT study (number of detected lesions, TNM stage, clinical performance and accidental findings)

Secondary: image quality (rating image quality, diagnostic confidence, normal tissue appearance, lesion contrast and relation with EANM procedure guidelines)

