## 2. OBJECTIVES

### 2.1 Primary objectives: lesion detection properties

*How does the diagnostic outcome of the digital PET/CT study compare to the outcome of conventional PET/CT in patients referred for (re)staging of lung cancer, breast cancer and esophageal cancer? In other words: does digital PET detect more, the same or less abnormalities in patients with cancer.*

*More in detail:*

- 1.1 What is the difference in the number of lymph node metastases?
- 1.2 What is the difference in the number of involved lymph node stations?
- 1.3 What is the difference in the N status?
- 1.4 What is the difference in the number of distant metastases?
- 1.5 What is the difference in the number of involved distant metastatic systems (e.g. bone, brain, adrenals, liver, lungs)?
- 1.6 What is the difference in the M status?
- 1.7 What is the overall difference in final TNM classification?
- 1.8 Using a composite reference standard, what is the sensitivity, specificity and accuracy for lymph node staging, distant metastatic and overall staging of digital PET/CT as compared to conventional PET/CT?
- 1.9 Is there a difference in unrelated accidental findings?

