### **5.2.3 Validation**

For each patient, the results of the PET/CT studies will be compared with available validation results. It is preferred that this regards invasive staging with pathology (PA) evaluation, although it may also include follow-up or information from other imaging modalities such as MRI and contrast-enhanced CT. Validation shall be performed based on findings from both conventional and digital PET/CT.

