### **9.5 End of study report**

The investigator will notify the accredited METC of the end of the study within a period of 8 weeks. The end of the study is defined as the moment that 225 patients are included. In case the study is ended prematurely, the investigator will notify the accredited METC within 15 days, including the reasons for the premature termination. Within one year after the end of the study, the investigator will submit a final study report with the results of the study, including any publications/abstracts of the study, to the accredited METC.

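### Follow-up PET is part of the reference standard for objective 1.8, so the reference can repeat the index scan's errors and favour whichever scanner type made the follow-up scan

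*Combined protocol and SAP*

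**What the plan says.** Objective 1.8, one of the primary objectives in section 2.1, asks: "Using a composite reference standard, what is the sensitivity, specificity and accuracy for lymph node staging, distant metastatic and overall staging" of digital compared with conventional PET/CT. Section 3 gives the content of that reference: "Pathology results and follow-up imaging by PET, CT, echography and MRI will be used as gold standard".

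Section 5.2.3 ranks pathology first but no further: "It is preferred that this regards invasive staging with pathology (PA) evaluation, although it may also include follow-up or information from other imaging modalities". It adds: "Validation shall be performed based on findings from both conventional and digital PET/CT". For patients with no reference result, section 3 says: "When validation results are not available, conventional and digital PET/CT results are just compared with each other".

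Section 7.1.1 tests the differences in sensitivity, specificity and accuracy with McNemar's test. Section 7.1.2 (Optimal cut-off values) uses the same validation results for the ROC curves, the cut-offs and a further McNemar comparison.

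Section 9.5 says: "The end of the study is defined as the moment that 225 patients are included". It allows up to one more year for the final report.

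The documents do not say which scanner or reader supplies a follow-up PET, whether PET alone may confirm or refute a lesion, whether the reference is judged without knowledge of the index scans, or when collection of reference data stops.

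**The concern.** A reference standard should be able to contradict the test it judges. A second FDG-PET shares its mechanism with the first. The introduction itself notes that inflammation takes up FDG as tumours do. Persistent inflammatory uptake can therefore appear on both the index and the follow-up PET and be counted as disease. A lesion too small or too faint for one detector type can be missed twice and be counted as absent.

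Both errors raise the apparent accuracy of PET. They also bear on the comparison. McNemar's test depends only on the sites where the two scanners disagree, and a follow-up scan on one scanner type tends to side with the index scan of that type. Section 5.1.6 puts the digital images in the medical record and has scanner differences reported, so later readings need not be independent of the index result.

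At stake is whether a difference found under objective 1.8, or a cut-off derived under objective 2.5, reflects disease or agreement of PET with PET. Section 9.6 foresees use of the results for marketing and regulatory claims.

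**Working it through.** **The plan's own figures.** Objective 1.8 has no sample size or expected accuracy to reproduce. The sizes in section 4.4 do reproduce with an exact two-sided sign test at 0.70 and 0.66 against 0.50: 49 (power 0.810), 79 (0.807), 28 (0.682) and 42 (0.660). The targets 90 + 90 + 45 give 225. These sizes serve objectives 1.1 and 1.3, which compare scanner with scanner. The reference is not an input, so the present point does not touch them.

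**Illustration: inputs, all assumed because the documents give none.**
- Diseased sites: 0.70 seen on both scanners, 0.10 on digital only, 0.10 on conventional only, 0.10 on neither. True sensitivity is 0.80 for each.
- f = share of sites whose status comes from follow-up PET: 0.2 to 0.3.
- r = probability that follow-up PET repeats a miss of the same scanner type: 0.8. Otherwise it shows the truth, and positive calls are always confirmed.
- d = share of follow-up PET made on the digital scanner, unrelated to which index scan saw the site.

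**Probability that a diseased site is labelled positive by the reference.**
- Seen on both: 1
- Digital only: 1 − f·r·(1 − d)
- Conventional only: 1 − f·r·d
- Neither: 1 − f·r

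**All follow-up PET digital (d = 1).**
- f = 0.2: f·r = 0.16. Reference positives = 0.70 + 0.10 + 0.084 + 0.084 = 0.968. Digital 0.800/0.968 = 82.6%; conventional 0.784/0.968 = 81.0%. Difference 0.016/0.968 = 1.7 points. Discordant ratio 0.100/0.084 = 1.19.
- f = 0.3: f·r = 0.24. Reference positives = 0.70 + 0.10 + 0.076 + 0.076 = 0.952. Digital 0.800/0.952 = 84.0%; conventional 0.776/0.952 = 81.5%. Difference 0.024/0.952 = 2.5 points. Ratio 0.100/0.076 = 1.32.

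**75% digital (d = 0.75).**
- f = 0.2: (0.096 − 0.088)/0.968 = 0.8 points; ratio 1.09.
- f = 0.3: (0.094 − 0.082)/0.952 = 1.3 points; ratio 1.15.

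**Even split (d = 0.5).** The two discordant cells shrink equally, so the difference is 0 and the ratio 1.0. Both sensitivities are still inflated: 0.792/0.968 = 81.8% and 0.788/0.952 = 82.8%, against a true 80%.

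**Sensitivity to the repeat rule.** Suppose a digital follow-up PET repeats positive and negative calls alike with probability 0.8 and otherwise reverses them.
- f = 0.2: (0.096 − 0.084)/0.936 = 1.3 points; ratio 1.14.
- f = 0.3: (0.094 − 0.076)/0.904 = 2.0 points; ratio 1.24.

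**Benign sites.** If the reference repeats a false positive with probability c, that site leaves the reference negatives, and apparent specificity is sp/[1 − (1 − sp)·f·c]. With sp = 0.80, f = 0.3 and c = 0.5 this is 0.80/0.97 = 82.5%.

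**The case against.** **Pathology is preferred and often available.** Section 5.2.3 puts it first, findings from either scanner trigger validation, and section 1 gives frequent invasive staging as a reason for choosing these tumours. This stands, and it confines the problem to lesions and patients without pathology. Their share is not given. The preference does not settle what happens when PET is the only later evidence.

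**A reader might infer that the reference favours digital.** The documents do not support that. Section 3 does not name the scanner used for follow-up PET. The Summary says only: "For a period of 6-12 months, both a conventional and a digital PET/CT system will be available in the NM department in Isala". Digital follow-up is plausible after that period, but it is an assumption, and the direction of the bias rests on it. With mostly conventional follow-up PET the sign would reverse.

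**A reader might infer from section 9.5 that follow-up ranges from many months for early patients to none for late ones.** With 6-12 months of accrual that would hold if reference collection closed at the 225th inclusion. But that sentence serves notification of the ethics committee, and the same section allows a further year to the final report. The documents leave the window undefined. A patient with no reference result is not scored against an empty reference; under section 3 that patient leaves the objective 1.8 analysis. A window that differs between patients would therefore act mainly through selective verification. Because both scans of a patient share one reference, it would not by itself favour either scanner.

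**It might be said that the small lesions seen on one scanner are the ones least likely to have pathology.** That may be so, but the documents give no figure and the point does not need it.

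**The study is an initial assessment, and objective 1.8 is not formally sized.** True, and this limits the weight of any single test. Objective 1.8 is still listed as primary.

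**Conclusion.** The concern holds in a limited form. Section 3 admits follow-up PET to the reference for a comparison of two PET scanners, and nothing elsewhere restricts its role. Where pathology is absent, repeated false positives and repeated misses can be scored as truth. This inflates apparent accuracy and tilts the comparison towards the scanner type that made the follow-up scan.

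Under the assumed inputs, the spurious sensitivity difference is about 1.7-2.5 points towards digital with all-digital follow-up, 0.8-1.3 points at 75% digital, and zero at an even split. It is about 1.3-2.0 points with all-digital follow-up if the 80% repeat rate applies to both kinds of call. The shares, the repeat rate and the scanner mix are all assumptions, so these figures show scale and do not predict the trial's bias.

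The scope is objective 1.8 and the cut-off analysis for objective 2.5. Objectives 1.1 and 1.3 and the total of 225 stand. The missing reference window is a secondary point that needs clarification; it does not show that late patients go without follow-up.

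**What to change.** 1. Keep the composite reference and the preference for pathology. For each lesion or patient, record which source settled the reference status and, for follow-up PET, which scanner was used.
2. Before the reference data are read, specify a repeat of the objective 1.8 McNemar comparison and of the cut-off analysis that counts only pathology or non-PET imaging. Report it beside the composite result. If a digital gain appears only with the composite, describe it as dependent on PET-based verification. The repeat should not be a pass-or-fail condition for a claim, because the subset is smaller, unsized and selectively verified.
3. As a clarification, state one common window for collecting reference data in all patients and the date on which collection closes. A window of up to one year for the last patient can fit within the reporting period of section 9.5.

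The cost is one extra recorded field (two items where the source is PET) and one extra analysis, with no additional patient procedures. The drawback is fewer verified lesions and wider intervals in the non-PET analysis.
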